8.8.4. Follow-Up Period

Follow-up visits will be conducted on Days 21, 28, and 35 with a final study visit on Day 49 (or early termination). Based on their preference, the subject will either come into the study center, or the qualified home healthcare provider will come to the subject's home on Days 21, 28, and 35. The final study visit will be conducted at the study center.

8.8.4.1. Follow-Up Visits: Days 21, 28, and 35

The following procedures will be performed on Days 21, 28, and 35 (-8 hours/+3 days for Days 21, 28, and 35):

- Collect blood samples for PD biomarkers at approximately 168 hours (-8 hours/+3 days), 336 hours (-8 hours/+3 days), and 504 hours (-8 hours/+3 days) postdose (for Cohort 4, all times are relative to evening dosing).
- Collect blood samples for PK at approximately 168 hours (-8 hours/+3 days), 336 hours (-8 hours/+3 days), and 504 hours (-8 hours/+3 days) postdose (for Cohort 4, all times are relative to evening dosing).
- AE monitoring.

• Record concomitant medications.

At each visit, subjects will be reminded to notify the investigator or study staff by telephone if they experience any AEs and before taking any concomitant medications.

At the Day 35 visit, subjects will be reminded to report to the study center on Day 49 (+7 days) for the final study visit (or at early termination).

8.8.4.2. Final Study Visit: (Day 49 [+7 Days] or Early Termination)

Subjects will return to the study center for the final study visit.

The following procedures will be conducted at the final study visit:

- Perform a physical examination including weight.
- Collect vital signs.
- Perform 12-lead ECG in triplicate (1-3 minutes apart).
- Perform a urine pregnancy test (β -hCG) for female subjects of childbearing potential.
- Collect blood sample for hematology and clinical chemistry.
- Collect urine sample for urinalysis.
- Collect blood sample for PD biomarkers.
- Collect blood sample for PK.
- Administer the BPRS.
- Administer the C-SSRS (Since Last Visit version).
- AE monitoring.
- Record concomitant medications.

8.9. Study Duration

The total duration of the study (including screening, a 24-hour PD baseline period, treatment periods, and follow-up) will be approximately 11 weeks, including up to approximately 3 weeks for screening, a 24-hour PD baseline period (approximately 7 days prior to the first day of dosing), 14 days of dosing, and a follow-up period of approximately 5 weeks. The total duration of the study will be an additional 8 to 11 weeks for subjects who reenroll.

8.10. **Prohibitions and Restrictions**

8.10.1. Prior and Concomitant Medications

All prescription and over-the-counter medications, dietary supplements (including vitamins), and herbal supplements taken by the subject during the 30 days before screening will be recorded on the Prior and Concomitant Medications page of the eCRF.

Subjects must be on a stable regimen of steroidal treatment for CAH for a minimum of 30 days before PD baseline (Day -7) and the regimen should remain stable throughout the study.

the case of intercurrent stressful events, appropriate corticosteroid augmentation should be provided.

Female subjects of childbearing potential may use

In

hormonal contraception during the study if taken for at least 3 months prior to screening. Subjects who are on stable medication regimens to treat stable medical conditions (other than CAH) are allowed to participate in the study. Use of cannabis products for a substantiated medical use (ie, not recreational use) is permitted during the study.

The following medications are prohibited from 30 days before screening until the final study visit (or early termination):

- Dexamethasone
- Orally administered glucocorticoids for indications other than CAH
- As-needed doses of anxiolytics

Before excluding any subject based on prior and concomitant medication use, please contact the NBI Medical Monitor. Any concomitant medication taken during the study will be recorded on the Prior and Concomitant Medications page of the eCRF with indication, total daily dose, route, and dates of drug administration.

Any additions, deletions, or changes in the dose of medications during the study should be recorded on the appropriate eCRF page.

8.10.2. Dietary and Other Restrictions

Subjects may be confined to the study center for approximately 24 hours two (Cohorts 3 and 4) or three (Cohorts 1 and 2) times during the study; on Days -7 to -6 (for PD baseline sample collection), Days 1 to 2 (Cohorts 1 and 2 only), and Days 14 to 15. In these instances, subjects will be discharged from the study center after completion of the required procedures. On Days 1 and 14 for Cohorts 1 and 2, subjects will go to bed after study drug dosing at approximately 2200 hours and will be awakened the next morning (Days 2 and 15, respectively) at approximately 0600 hours. Subjects in Cohorts 3 and 4 will receive the study drug with a moderate fat/moderate calorie meal at approximately 1900 hours on Day 14. This meal must be consumed within 30 minutes of taking study drug.

Foods containing poppy seeds are prohibited from 7 days before screening until the final study visit. Subjects must refrain from excessive consumption of alcohol (ie, no more than 2 drinks per day) during the study.

Strenuous activity beyond what is customary for the subject is prohibited during the study.

Subjects must not donate blood or blood products from 30 days before Day -7 until 30 days after the final study visit (or early termination). Male subjects must agree to refrain from donating sperm for 90 days after the last dose of study drug.

Participation in another investigational drug study is prohibited for at least 30 days after the last dose of study drug in the current study.

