Subjects in Cohorts 3 and 4 will have a blood sample collected on Day 1 for (only for subjects who have not previously participated in Cohorts 1 or 2). Baseline safety assessments will be collected on Day 1 prior to the first dose of study drug. For Cohort 3, study drug (NBI-74788 100 mg) will be administered at home on Days 1 to 13 at approximately 1900 hours with each subject's evening meal. For Cohort 4, study drug (NBI-74788 100 mg) will be administered at home on Days 2 to 14 at approximately 0700 hours with each subject's breakfast and on Days 1 to 13 at approximately 1900 hours with each subjects' evening meal. For both cohorts, the Day 14 evening dose will be administered at the study site. Subjects will take their usual morning dose of concurrent steroidal treatments at approximately 1000 hours on Days 1 to 14. On Day 7 during the treatment period, PK, PD, and safety assessments will be conducted in an outpatient setting at the study center. Subjects will be admitted to the study center on Day 14 (last day of dosing). On Day 14, subjects will receive study drug in the study center at approximately 1900 hours with a standard (moderate fat/moderate calorie) evening meal. The subjects' usual morning dose of concurrent steroidal treatments will be administered after PK/PD samples are collected at approximately 1400 hours on Day 15. Subjects will be discharged from the study center the evening on Day 15 following completion of all studyrelated procedures.

Standard meals and snacks will be provided by the study center during the in-patient stays.

For all cohorts, follow-up visits on Days 21, 28, and 35 will be conducted at the study center or the subject's home by a qualified home healthcare provider (based on the subject's preference). A final study visit will be conducted at the study site approximately 5 weeks after the last dose of study drug (on Day 49 or early termination). There will be a visit window of -8 hours for Day 7, -8 hours/+3 days for Days 21, 28, and 35, and +7 days for the final study visit. Safety, tolerability, PK, and PD will be assessed at scheduled times throughout the study.

The study design schematic is shown in Figure 1.

Figure 1: Study Design Schematic

bid=twice daily.

Visits on Days 21 (+3 days), 28 (+3 days), and 35 (+3 days); final study visit on Day 49 (+7 days) or early termination.

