8.7.2. Day -7 to Day -6: 24-Hour Baseline Pharmacodynamics

Subjects who continue to meet eligibility requirements will return to the study center for a 24-hour in-patient stay, during which blood samples will be collected for PD analysis. Subjects will not take their usual morning dose of steroidal treatment until after the 1000 hours PD sample is collected on Day -6.

The following study evaluations and tasks will be performed on Day -7 to Day -6:

- Update inclusion/exclusion criteria and medical history.
- Collect vital signs.
- Perform a urine pregnancy test (β -hCG) for female subjects of childbearing potential.
- Collect urine for drug screen and perform alcohol breath test. Urine testing kits will be provided by the central laboratory to confirm negative drug screen prior to PD collection. A separate urine sample will also be sent to the central laboratory for analysis.
- Collect blood samples for PD biomarkers (17-OHP, androstenedione, testosterone, cortisol, and ACTH) at: approximately 2145, 2300, 2400, 0100, 0200, 0400, 0600, 0800, 1000, 1200, 1400, 1800, and 2200 hours.
- AE monitoring.
- Record prior medications.

Eligible subjects will be instructed to return to the study center on Day 1.

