8.8.2. Day -7 to Day -6: 24-Hour Baseline Pharmacodynamics

Subjects who reenroll and do not undergo screening must provide subject informed consent.

Subjects who continue to meet eligibility requirements will return to the study center for a 24-hour in-patient stay, during which blood samples will be collected for PD analysis. Subjects will not take their usual morning dose of steroidal treatment until after the 1000 hours PD sample is collected on Day -6.

The following study evaluations and tasks will be performed on Day -7 to Day -6:

- Update inclusion/exclusion criteria and medical history (only for subjects who undergo screening).
- Collect vital signs.
- Perform a urine (for subjects who undergo screening) or serum (for subjects who did not undergo screening) pregnancy test (β-hCG) for female subjects of childbearing potential.
- Collect urine for drug screen and perform alcohol breath test. Urine testing kits will be provided by the central laboratory to confirm negative drug screen prior to PD collection. A separate urine sample will also be sent to the central laboratory for analysis.
- Collect blood samples for PD biomarkers (17-OHP, androstenedione, testosterone, cortisol, and ACTH) at: approximately 1845, 2000, 2100, 2200, 2300, 2400, 0100, 0200, 0400, 0600, 0800, 1000, 1200, 1400, 1800, 1900, and 2200 hours.
- Administer the C-SSRS (Screening/Baseline version) only for subjects who reenroll and who do not undergo screening.
- AE monitoring.
- Record prior medications.

Eligible subjects will be instructed to return to the study center on Day 1.

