9.3. Study Drug Administration

Cohorts 1 and 2

Subjects will take study drug capsule(s) by mouth at approximately 2200 hours for 14 consecutive days beginning on Day 1. Each dose of study drug is to be administered with a bottle of vanilla-flavored (~237 mL); subjects should finish consuming the entire bottle of within 30 minutes of taking study drug. The designated NBI-74788 dose (50 or 100 mg) will be administered as 1 or 2 NBI-74788 50 mg capsules.

Cohort 3

Subjects will take study drug capsules by mouth at approximately 1900 hours for 14 consecutive days beginning on Day 1. Each dose of study drug is to be administered with their evening meal; subjects should complete their evening meal within 30 minutes of taking study drug. The designated NBI-74788 dose (100 mg) will be administered as 2 NBI-74788 50 mg capsules.

Cohort 4

Subjects will take study drug capsules by mouth for 14 consecutive days beginning at approximately 1900 hours on Day 1; subsequently, study drug will be taken at approximately 0700 hours (with breakfast) and approximately 1900 hours (with evening meal). Subjects should complete their respective meals within 30 minutes of taking study drug. The designated NBI-74788 dose (100 mg) will be administered as 2 NBI-74788 50 mg capsules (200 mg total daily dose).

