12.7. Pharmacodynamic Data

The primary PD assessments are: morning 17-OHP (serum; ng/dL) from the 0600, 0800, and 1000 hour samples (8-, 10-, and 12-hour postdose samples from Cohorts 1 and 2 and 11-, 13-, and 15-hour postdose samples from Cohorts 3 and 4). Secondary PD assessments are: 17-OHP at all other times, androstenedione (serum; ng/dL), testosterone (serum; ng/dL), cortisol (serum; μ g/dL), and ACTH (plasma; pg/mL).

The PD assessments listed above will be summarized with descriptive statistics (including change from predose) and in graphical displays by dose cohort and timepoint.

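### Evening food on the Day -7 baseline night is not set to match the treatment profile nights, so any food effect on the PD markers cannot be separated from the drug effect

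*Combined protocol and SAP*

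**What the plan says.** **Food on treatment nights.** For Cohorts 1 and 2, Section 9.3 reads "Each dose of study drug is to be administered with a bottle of vanilla-flavored (~237 mL" (the product name is blacked out). The bottle is to be finished within 30 minutes of a dose taken at about 2200. This covers the Day 1 and Day 14 profile nights. For Cohort 3 the same section reads "Each dose of study drug is to be administered with their evening meal", and Cohort 4 doses go with breakfast and the evening meal. Home meals are the subject's own. Only the Day 14 evening meal is standardised, in Section 8.10.2: "Subjects in Cohorts 3 and 4 will receive the study drug with a moderate fat/moderate calorie meal at approximately 1900 hours on Day 14". It is eaten within 30 minutes of dosing.

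**Food on the baseline night.** In Section 8.7.2, subjects in Cohorts 1 and 2 "will return to the study center for a 24-hour in-patient stay, during which blood samples will be collected for PD analysis". The task list there contains no bottle. Section 8.8.2 has the parallel sentence for Cohorts 3 and 4, "Subjects who continue to meet eligibility requirements will return to the study center for a 24-hour in-patient stay", and sets no evening meal time or content. Section 6.1 has a general rule: "Standard meals and snacks will be provided by the study center during the in-patient stays".

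**Endpoint and analysis.** Section 12.7 names the primary PD assessment as "morning 17-OHP (serum; ng/dL) from the 0600, 0800, and 1000 hour samples" and places these at "8-, 10-, and 12-hour postdose samples from Cohorts 1 and 2 and 11-, 13-, and 15-hour postdose samples from Cohorts 3 and 4". Change is summarised descriptively, relative to a predose value that is not defined. Section 7.4 describes the study as single-arm.

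**The concern.** In an uncontrolled before-after comparison, any condition that changes systematically between the two profiles is absorbed into the estimated drug effect. The sponsor matched the blood sampling by clock time, which shows that a like-for-like comparison was intended. Evening food was not matched in the same way.

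Followed exactly as written, the plan gives every Cohort 1 and 2 subject a bedtime drink on the profile nights and schedules none at baseline. In Cohorts 3 and 4 the two evenings may or may not be alike, because only one of them is specified. If evening intake affects overnight ACTH or 17-OHP in these subjects, the reported change would carry that effect as well. Whether it does is an assumption, on which the documents are silent.

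**Working it through.** The plan states no food effect, effect size or SD, so there is no figure to reproduce. The check sets the stays side by side and then shows how an unknown shift would carry through.

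**1. Evening food on each profile night**

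| | Day -7 baseline | On-treatment profile |
|---|---|---|
| Cohorts 1 and 2 | Standard meals and snacks (6.1); no bottle listed (8.7.2) | Bottle of about 237 mL at about 2200, Days 1 and 14 (9.3) |
| Cohorts 3 and 4 | Standard meals and snacks (6.1); evening meal time and content not stated (8.8.2) | Moderate fat, moderate calorie meal at about 1900, Day 14 (8.8.3.3, 8.10.2) |

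**2. Sampling is clock-matched.** In Cohorts 1 and 2 the baseline runs from 2145 to 2200 the next day, which is -0.25 to 24 hours from a 2200 dose. In Cohorts 3 and 4 (Section 8.8.2) it runs from 1845 to 2200 the next day, which is -0.25 to 27 hours from a 1900 dose. Both agree with the Day 14 to 15 schedules.

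**3. Is there another drug-free reference?**
- Cohorts 3 and 4 have no Day 1 PD sample (Table 3), and their Day 14 predose sample follows 13 days of dosing.
- Cohorts 1 and 2 have a Day 1 predose sample, but it is one evening value at about 2145. It matches neither the 0600 to 1000 window nor the post-bottle condition.
- Their Day 1 and Day 14 profiles match each other on the bottle, but both follow a dose.
- Screening gives one morning 17-OHP value, not a profile, and some re-enrolled subjects skip it.

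That leaves Day -7 to -6 as the only drug-free, clock-matched profile, whatever predose is taken to mean.

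**4. Time from food to sample.** Bottle at 2200: the 2300 to 0200 samples fall 1 to 4 hours later, and the 0600, 0800 and 1000 samples 8, 10 and 12 hours later. Meal at 1900: the 2000 to 2400 samples fall 1 to 5 hours later, and the primary samples 11, 13 and 15 hours later.

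**5. Illustration.** Let d be the true proportional fall and s the proportional food-related shift. Both values are assumed: d = 0.30, and s between 5% and 20% in either direction.

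Apparent fall = 1 - (1 - d)(1 + s)

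- s = -0.05: 1 - 0.70 x 0.95 = 0.335
- s = -0.20: 1 - 0.70 x 0.80 = 0.440
- s = +0.05: 1 - 0.70 x 1.05 = 0.265
- s = +0.20: 1 - 0.70 x 1.20 = 0.160

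**The case against.** The strongest reply is that nothing in the documents shows food moves these hormones. The primary samples are taken 8 to 15 hours after the evening food, the samples nearest to it are secondary, and every summary is descriptive, so there is no formal test to distort. The drink's identity is blacked out and its composition cannot be judged. All of this stands, and it keeps the point small.

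It can also be said that the reference for change is undefined, so the baseline profile may not be the comparator. That does not remove the gap, because no other drug-free profile exists.

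A reader might infer four stronger things that the documents do not support:
- **That subjects have no food at baseline.** The general rule in Section 6.1 covers in-patient stays, and the baseline is one. In Cohorts 3 and 4 the evening meal is unspecified, not absent.
- **That food is fixed on all treatment nights in Cohorts 3 and 4.** It is standardised only on Day 14, although that night begins their only serial on-treatment profile.
- **That breakfast differs between Day -6 and Day 15.** Its time is fixed on neither day, and equal silence shows no mismatch.
- **That bottle versus meal spoils the comparison of regimens.** The accompanying food is part of how each cohort's regimen is defined in Section 6.1.

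**Conclusion.** The point holds as a minor comparability gap. In Cohorts 1 and 2 the bottle is present on the profile nights and not scheduled at baseline. In Cohorts 3 and 4 the Day -7 evening meal is not stated to match the Day 14 meal in time or content. With no control arm and only one usable drug-free profile, any resulting effect cannot be separated from the drug effect.

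Neither the size nor the direction can be computed from the documents. The assumed 5% to 20% shift around a true 30% fall spans readings from 16% to 44%, so the effect could be diluted as easily as inflated. A reader might infer that the drug effect is overstated, but nothing supports choosing that direction. The illustration also applies the full shift, which is more plausible for the early post-dose secondary samples than for the primary 0600 to 1000 samples. This is a cheap improvement, not a threat to the study's main descriptive findings.

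**What to change.** In Section 8.7.2, schedule the same bottle at about 2200 on Day -7 for Cohorts 1 and 2. In Section 8.8.2, serve the same standard evening meal as on Day 14 at about 1900 on Day -7 for Cohorts 3 and 4.

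The cost is one bottle or one timed meal per subject at a stay that already takes place, plus the wording. Cohort 3 and 4 subjects must already be at the center for the 1845 sample, and exclusion criterion 25 already screens Cohorts 1 and 2 for intolerance to the drink. No dose or clinical rule changes. Where a baseline profile has already been collected without matched food, the report should say so as a limitation.

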8.11. Withdrawal Criteria

8.11.1. Reasons for Withdrawal

Subjects are free to discontinue their participation in the study at any time. The investigator must withdraw any subject from the study if that subject requests to be withdrawn.

The investigator must withdraw the subject from the study if the subject experiences any of the following:

- If the type, frequency, or severity of any AE becomes unacceptable/intolerable.
- QTcF value >500 msec (one or more value; cardiologist verified).
- Is lost to follow up.
- Subject is confirmed to be pregnant.

The investigator or NBI may withdraw the subject from the study for other reasons as described below. These should be discussed on a case-by-case basis with the NBI medical monitor (or designee) prior to withdrawing the subject from the study.

- Develops an ECG abnormality.
- Liver function test values for AST or ALT exceed 2.5 times ULN, GGT exceeds 3 times ULN, or total bilirubin exceeds 2 times ULN.
- Creatinine value exceeds 1.5 times ULN.

- Positive urine drug or alcohol screen.
- Requires a medication that is prohibited by the protocol (refer to Section 8.10.1).

All subjects prematurely discontinuing the study, regardless of cause, should have all early termination assessments performed (see Section 8.7.4.2).

8.11.2. Handling of Withdrawals

If a subject prematurely withdraws from the study, either at his/her request or at the investigator's discretion, the investigator will record the reason for withdrawal on the relevant eCRF. All subjects who withdraw from the study prematurely will be asked to have all early termination assessments performed within 4 weeks.

It is crucial to obtain follow-up data for any subject withdrawn because of an AE, abnormal laboratory test, vital sign measurement, physical examination, or ECG finding. In any case, every effort must be made to undertake safety follow-up procedures.

8.11.3. Sponsor's Termination of Study

NBI reserves the right to discontinue the study at any time for clinical or administrative reasons. Such a termination must be implemented by the investigator if instructed to do so by NBI in a time frame that is compatible with the subjects' well-being.

9. STUDY DRUG

NBI-74788 will be supplied as capsules containing 50 mg of NBI-74788 for oral administration.

9.1. Study Drug Supplies

NBI or its designee will provide the study site with sufficient capsule supplies for the completion of the study. Study drug will be supplied in subjects with bottles of vanilla-flavored (~237 mL) (Cohorts 1 and 2 only).

9.2. Study Drug Packaging and Labeling

All packaging and labeling operations will be conducted according to Good Manufacturing Practice (GMP) and GCP. The study drug will be sent to designated staff at the study site who must complete and return the Drug Supply Confirmation to NBI or its designee verifying the receipt of the drug.

Study drug will be labeled with the following information, including, but not limited to: protocol number, dosage form, route of administration, Sponsor name, and the statement "Caution – New Drug: Limited by Federal law to investigational use."

